**Background**

The detrimental impacts of cognitive impairment

Dementia is an irreversible devastating neurodegenerative disorder characterized by memory loss, cognitive deterioration, functional impairment and behavioral changes. Alzheimer's disease is the most common type, accounting for 60-80% of late-life dementia.[16, 17] Dementia imposes not only significant physical and psychological burdens on the sufferers and their families but also enormous service demands on health and social care systems. Because dementia is an incurable and progressive debilitating chronic condition, it is imperative to develop effective means by which to mitigate disease burden at the pre-dementia stage. Mild cognitive impairment (MCI) represents the reversible, intermediate clinical state between normal age-related cognitive decline and dementia, but it does not fulfill the diagnostic criteria for dementia.[3, 18] It is a highly prevalent condition, particularly among the geriatric population. A meta-analysis including 34 epidemiologic studies reported the prevalence of MCI ranged from 8.4% for people aged 65-69 years to 25.2% for those aged 80-84 years.[20] Solid epidemiological evidence suggests that MCI persons are prone to progress to dementia, most often Alzheimer's disease, at a rate of 10 to 15% per year.[18] These data highlight the urgent need to identify effective and safe strategies to halt or even reverse the progression of cognitive impairment in MCI persons.

Insomnia in MCI persons

At present, no pharmacological treatment has proved to be effective in reversing cognitive impairment in MCI persons. Instead, modification of risk factors remains the primary strategy to reshape the cognitive trajectory in these persons. Empirical evidence has linked several lifestyle and vascular risk factors to an increased risk of cognitive decline in MCI and Alzheimer's disease.[22] Accordingly, research evidence is accumulating to support the empirical effects of risk modification interventions in improving the cognitive health of MCI persons, such as engagement in physical, social and cognitive activities.[23-25] Indeed, growing evidence is emerging to suggest insomnia as a new risk factor to be associated with cognitive decline and conversion from MCI to dementia.[5] Insomnia symptoms, including difficulty in falling asleep, waking up during the night and early morning awakening, are highly prevalent among MCI persons but have received the least attention. [27] Epidemiological evidence also suggests that poor sleep is associated with an increased risk of converting from MCI to dementia.[30]

The underlying mechanisms linking sleep to cognition

General and condition-specific mechanisms underlie the connection between sleep and cognition. Generally, sleep serves a restorative function in the brain to maintain normal cognitive function. In particular, slow-wave sleep (i.e., deep sleep) is essential for memory consolidation, a crucial process that stabilizes and fully integrates memory traces into long-term memory. Studies have documented that changing the sleep architecture by reducing the time in slow-wave sleep result in memory loss.[6, 31] Specifically, the underlying mechanisms linking sleep and cognition are related to the deposition of amyloid- $\beta$  in the brain, the hallmark histopathological change in Alzheimer's disease. A poor sleep increases the level of amyloid- $\beta$  release over time and augments amyloid- $\beta$  deposition,[8] thus entailing an increased chance of amyloid plaque accumulation and subsequently contributing to early cognitive decline and conversion to dementia through the disruption of hippocampus-dependent memory.[9] The aforementioned vicious cycle between disturbed sleep and amyloid- $\beta$  pathology underscores the potential cognitive benefits of interventions to improve sleep among MCI persons.

### Sleep promotion in MCI persons: an unaddressed issue

Pharmacotherapy remains the most common sleep aid modality for managing insomnia in adults. However, hypnotic drugs are typically not suggested for long-term use in an older population because of the increased risk for adverse effects, drug-drug interactions, dependence, tolerance and the lack of empirical evidence to support their long-term efficacy in this population.[33] Their common side effect of reducing cognitive performance further compromises their use among the MCI population.[34] Thus, the use of non-pharmacological approaches should be a priority to promote better sleep in this clinical population. Among such strategies, cognitive-behavioral therapy for insomnia (CBT-I) has received the best recognition in the literature.[11, 35]

CBT-I is a multi-component approach that combines various cognitive and behavioral strategies including sleep restriction, stimulus control, cognitive therapy, sleep hygiene and relaxation strategies. The underlying assumption of this non-pharmacological treatment is based on Spielman's 3P Model of Insomnia, which delineates the roles of predisposing, precipitating and perpetuating factors in hampering effective sleep function.[36] CBT-I comprehensively tackles these factors that maintain insomnia over time through the following five key intervention components:

1. Stimulus control: a set of behaviors aimed at strengthening the association between the bedroom and other environmental cues with rapid sleep onset.
2. Sleep restriction: a technique to consolidate sleep by limiting the time spent in bed to the actual time of sleeping. An initial sleep deprivation is induced to increase sleep efficacy and is followed by a gradual prolongation of the sleeping time.
3. Sleep hygiene: teaching lifestyle habits that are more conducive to sleeping and avoiding sleep-incompatible behaviors.
4. Relaxation training: a technique used to induce a complete state of physical and mental relaxation and hence reduce cognitive, emotional and physiological arousal that is non-conducive to sleeping.
5. Cognitive restructuring: a technique to alter faulty beliefs and attitudes that often serve to exacerbate insomnia and replace them with more adaptive substitutes.

The sleep-promoting effects of CBT-I have been widely examined in clinical trials.[12] Because it addresses a variety of perpetuating factors of insomnia, CBT-I was found to be more effective than a single-component approach in tackling insomnia.[11] As such, the international guideline from the American College of Physicians has recommended the wide application of CBT-I to manage chronic insomnia in general adults.[11] Despite such strong recognition of the sleep-promoting effects of CBT-I, its application in people with MCI is minimal. The compromised cognitive ability of this group and, thereby, the resulting challenges in their active engagement may explain such limited application.

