### Study design

This will be a mixed-method study with a single-blinded parallel-group randomized controlled trial (RCT) and a qualitative study to determine the feasibility and preliminary effects of the empowerment-based CBT-I on sleep, cognitive outcomes and HRQoL in persons with MCI. The study implementation protocol is outlined in Figure 1. A research assistant (RA1) will recruit eligible participants from the elderly community centers operated by two non-governmental organizations in Hong Kong. After collecting the baseline data (T0), RA1 will randomly assign participants into the intervention group and control group with block randomization to ensure even distribution of participants in the two study groups over the study period. A computer-generated random sequence will be used to determine the block size (6, 8 and 10) and respective study group allocation in a 1:1 ratio. To ensure allocation concealment, the group allocation will be determined according to the random sequence codes placed in sealed opaque envelopes. Participants in the intervention group will receive the empowerment-based CBT-I, whereas the control group will receive usual care. To minimize biases, another research assistant (RA2) who is blinded to the group allocation will be responsible for collecting post-test data immediately (T1) and 3 months (T2) post-intervention for both groups. A total of 10 participants, with 3-4 participants from each intervention group, will be invited to take part in a qualitative interview to obtain more in-depth comments about the feasibility and acceptability of the intervention.

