Participants in the intervention group will participate in a 12-week empowerment-based CBT-I comprising face-to-face sessions supplemented with telephone follow-ups. In total, six face-to-face sessions (90 minutes/session) will be conducted in a small group format with 6–8 participants in a group and two 30-minute individual sessions will be scheduled over eight weeks, with the individual sessions arranged in the 4th and 7th week, and this is then followed by two bi-weekly telephone follow-ups. The face-to-face delivery modality is adopted to meet the challenges of mildly impaired cognition faced by MCI persons, whereas the small group format was chosen in accordance with the literature suggesting it has efficacy comparable with the individual format.[50] The group format is more cost-effective, and it can facilitate peer modeling and learning. The face-to-face sessions will cover the following core areas in CBT-I: i) sleep education, ii) sleep hygiene and relaxation, iii) sleep restriction, iv) stimulus control and v) cognitive therapy. The first five sessions will cover these core areas, and a booster session will then follow to summarize the key components of CBT-I and equip the participants with relapse-prevention strategies when sleeping problems recur (Table 1). The content of the CBT-I components complies with the recommendations for managing chronic insomnia by major international sleep associations.[11, 51]

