### **Outcome measures**

Sleep assessment. Three measures were chosen to evaluate sleep pattern and quality by both subjective and objective means according to the recommendations suggested by the international expert consensus.[52] The 19-item Chinese version of the PSQI will be used to assess subjective sleep quality.[53] It is reliable (Cronbach's alpha = 0.83) and has shown good test-retest reliability and discriminant validity.[53] The Chinese version of the Insomnia Severity Index (ISI-C) (7-item)[54] will be used to assess the perceived insomnia severity, consequences of insomnia and the degree of distress related to insomnia. A five-point Likert scale is used, with higher values indicating higher levels of perceived severity of insomnia, more severe consequences of insomnia and a greater degree of distress associated with insomnia. The ISI-C has good internal consistency (Cronbach's alpha = 0.81), construct and discriminant validity.[54] An Actiwatch, which contains an accelerometer to record the frequency and intensity of body movement, will be used to objectively assess sleep patterns. The parameters of sleep pattern include TST, SL, WASO and the ratio of TST to SE. Participants will be instructed to wear the Actiwatch on their non-dominant wrist during sleep for a consecutive seven-day period.

Cognitive assessments. To detect subtle cognitive changes, a battery of cognitive assessments will be used to evaluate various domains of cognition, including the Cantonese version of the Alzheimer's Disease Assessment Scale—Cognitive subscale (ADAS-Cog)[55] for global cognition, the digit span-forward and backward test for attention and working memory, the Hong Kong List Learning Test for episodic memory, and the Color Trails Test for complex attention, executive function and task switching.

HRQoL. The Chinese Hong Kong version of the Short Form Health Survey (SF-12) will be used to measure HRQoL.[56] It consists of 12 items to form two summary scores to reflect people's physical and mental well-being, with higher scores indicating better HRQoL. Its psychometric properties are satisfactory with evidence of good reliability, content and construct validity.[56]

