### **Ethical Consideration:**

This study followed the Declaration of Helsinki on medical protocol and ethics. Ethics approval will be obtained from the Institutional Review Board of the University of Hong Kong/Hospital Authority Hong Kong West Cluster. Patients are voluntary participants in the study. A written informed consent, which will include the research title, purpose, explanation of the research, and the procedures of the study, will be obtained from each eligible participant. Risks and benefits are also explained clearly to the participants.

Participants have the right to withdraw from the study at any time. They will be protected from discomfort and harm during the study. Further, anonymity and confidentiality of the participants will be strictly protected. Their decision of participating in the study will not affect the quality of present or future care they receive in the hospital.

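### The intervention includes sleep restriction, but adverse events are not systematically recorded or analysed in either arm, so the pilot could report feasibility without comparative adverse-event data

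*Combined protocol and SAP*

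**What the plan says.** The background section on sleep promotion in MCI lists five components of CBT-I. Of sleep restriction it says: "An initial sleep deprivation is induced to increase sleep efficacy", and it adds that sleeping time is then gradually lengthened. The intervention description makes this part of the trial treatment, since the core areas are "i) sleep education, ii) sleep hygiene and relaxation, iii) sleep restriction, iv) stimulus control and v) cognitive therapy". On timing it says: "The first five sessions will cover these core areas, and a booster session will then follow".

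The first aim, under Research plan and methodology, is feasibility. The same section makes sleep pattern and quality primary, and cognition and HRQoL secondary. Outcome measures opens with "Three measures were chosen to evaluate sleep pattern and quality by both subjective and objective means" (PSQI, ISI-C and Actiwatch) and adds a cognitive battery and the SF-12. Data analysis covers baseline comparisons and repeated-measures ANOVA, and does not mention harms.

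Study design has the blinded assessor (RA2) "collecting post-test data immediately (T1) and 3 months (T2) post-intervention for both groups". The other data come from the intervention arm: the therapist's (RA1's) session discussions and telephone records, attendance and fidelity checks, and interviews with 10 participants on feasibility and acceptability.

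Under Ethical Consideration the protocol undertakes, of participants: "They will be protected from discomfort and harm during the study". It does not say how harm would be detected or recorded.

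**The concern.** The plan delivers a component that, by its own description, begins by reducing sleep, to people with mild cognitive impairment and poor sleep. The background says CBT-I has had little use in this group, so its acceptance in general adults does not settle how well it is tolerated here. Tolerability is part of feasibility, and this pilot is meant to lead to a full-scale trial.

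If adverse events are not asked about in the same way in both arms, they cannot be reconstructed at analysis. The pilot could show better sleep scores and good attendance, be called feasible, and leave the next trial without event counts by arm to guide its monitoring.

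**Working it through.** **1. What each planned data source can show**

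| Source | Arms | Timing | Counts discrete adverse events? |
|---|---|---|---|
| PSQI, ISI-C, Actiwatch, cognitive battery, SF-12 | both | T0, T1, T2 | No; could show net worsening |
| Session discussions and telephone records | intervention | during treatment | Not systematically |
| Attendance and fidelity checks | intervention sessions and calls | during treatment | No |
| Interviews (10 people) | intervention | not stated | Not planned; feasibility and acceptability |

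No row gives adverse-event counts in both arms.

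**2. Timing**

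The programme is described this way: "Participants in the intervention group will participate in a 12-week empowerment-based CBT-I". The face-to-face phase lasts 8 weeks and two bi-weekly calls follow, so 8 + 2 × 2 = 12 weeks. The core areas are covered in the first five of six group sessions, within the 8-week phase. If T1 is at week 12, the PSQI's one-month window (about 4 weeks) reaches back to about week 12 − 4 = 8. The efficacy scales would then largely miss a transient problem while restriction is being introduced. The exact week of that session belongs to Table 1, which was not in the text available, so this timing is inferred.

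**3. The plan's own figure**

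The sample size is 60, or 2 × 30 at 1:1, which is consistent. No effect size, SD, power, dropout or event rate is given, so there is nothing further to reproduce.

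**4. What recording events would give**

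The event rates p are assumptions, because the documents give none. The n = 30 figures assume that all 30 in an arm are followed and every event is recalled.

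The chance of at least one event is 1 − (1 − p)^n. With n = 30:
- p = 2%: 1 − 0.98^30 = 45%
- p = 5%: 1 − 0.95^30 = 79%
- p = 10%: 1 − 0.90^30 = 96%

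The one-sided 95% upper limit with zero events is 1 − 0.05^(1/n). For 0/30 it is 1 − 0.05^(1/30) = 9.5%. The upper end of the two-sided exact 95% interval is 1 − 0.025^(1/30) = 11.6%.

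**5. Sensitivity to those assumptions**
- 25 of 30 followed (assumed): at p = 5%, 1 − 0.95^25 = 72%; the zero-event limit is 1 − 0.05^(1/25) = 11.3%.
- Half of events recalled (assumed): a 5% rate acts like 2.5%, so 1 − 0.975^30 = 53%.

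**6. Could the interviews substitute?**

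Even if they asked about harm, n = 10 gives 1 − 0.95^10 = 40% at p = 5%, and a zero-event limit of 1 − 0.05^(1/10) = 26%, in one arm only.

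**7. Should the arms be tested?**

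With 30 per arm and two-sided 0.05, the normal approximation gives power = Φ{(|p1 − p2| − 1.96·√[2p̄(1 − p̄)/30]) / √[(p1(1 − p1) + p2(1 − p2))/30]}, where p̄ is the mean of p1 and p2.
- 5% v 10%: Φ{(0.05 − 0.133)/0.068} = 11%
- 5% v 20%: Φ{(0.15 − 0.167)/0.083} = 42%
- 5% v 30%: Φ{(0.25 − 0.192)/0.093} = 73%

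Testing would be uninformative unless the difference were very large. Counts with exact intervals suit this size.

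**The case against.** A reader might infer that the trial measures no harm at all. The documents do not support that. Actiwatch total sleep time, insomnia severity with its consequences and distress, a battery meant to pick up small cognitive changes, and the SF-12 are collected in both arms by a blinded assessor and tested two-sided. Lasting deterioration at T1 or T2 could show.

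A reader might also infer that the protocol itself says sleep restriction may cause harm. It does not. It presents initial deprivation as part of how the technique works, followed by longer sleep, and nowhere links it to falls, sleepiness or accidents. The degree of deprivation in this trial is not known from the text, because the detail would sit in Table 1 and a manual still to be developed.

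Nor is it right that problems could never come to light. Later sessions open with challenges and barriers, group discussion covers feelings and concerns, individual sessions fall in weeks 4 and 7, and advice given by telephone is documented.

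All of this stands, and it limits the point. It does not remove it: the scales do not count events and are not taken during treatment, and the therapist's contacts are informal, unblinded and confined to one arm. The ethics sentence is an undertaking to participants, not a result that the pilot must prove. Risk wording on the consent pages is not judged here.

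**Conclusion.** The point holds in limited form. Sleep restriction is a core part of the intervention, and the plan does not systematically record or analyse adverse events or other safety outcomes in either arm. The pilot could therefore report feasibility without comparative adverse-event data, and data never collected cannot be recovered later. This is a gap worth closing at low cost. It is not evidence that the treatment is unsafe.

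The 79%, 96% and 9.5% figures show what complete recording in one arm could deliver. They rest on assumed event rates, full follow-up and full recall, and the sensitivity cases show how quickly they weaken. Even complete recording would support description only, not a test between arms.

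**What to change.** **Outcome measures.** Add a brief, neutrally worded, structured harms form covering falls, daytime sleepiness, accidents, other adverse events and the reason for any withdrawal. Give it identically to both arms at T1 and T2, after all other assessments. Have it self-completed and sealed, or otherwise kept from RA2, so that answers mentioning the treatment do not unblind RA2 before T2.

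**Intervention contacts.** Have RA1 log events at the existing sessions and calls. Report this log separately, because controls have no such contacts.

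**Data analysis.** Add counts by arm with exact 95% confidence intervals, descriptive only, and include them when feasibility is reported.

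**Cost.** A one-page form, a few minutes per visit and one table. Two weaknesses remain: people with memory complaints would be recalling events over a 12-week programme, and some unblinding risk persists. Brief identical contacts with both arms during treatment would ease the recall problem, but they would add contacts that the plan does not now have, so they are an option only. No change to the sleep-restriction procedure is proposed.

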### Engaging MCI persons in an active learning process: an empowerment approach

The empowerment approach has recently emerged as a novel, effective paradigm for health promotion and education. This person-centered collaborative approach optimizes learning by promoting patient participation during the educational process.[39] The essence of the empowerment model equips the therapist with a step-by-step approach to support the participants in understanding the rationale for behavioral changes; a goal-setting process to help them to stay focused and increase their motivation and autonomy;[14] and a subsequent process to assist the participants in developing an action plan as a roadmap to guide progressive goal attainment. The step of action planning also helps the participants to translate abstract knowledge and beliefs into concrete actions.[14] To the best of our knowledge, such an empowerment-based approach has never been used to compensate for the cognitive impairment in MCI persons that precludes the uptake of CBT-I content. Given the strong relationship between sleep and cognitive impairment, and the inadequacy of current empirical evidence on sleep-promoting interventions for MCI persons, we hypothesize that a multi-component CBT-I intervention featuring an empowerment-based approach would improve the sleep and cognitive function in this highly vulnerable group.

### Work done by us

This study is proposed to address the research gap identified by the investigation team. We are currently conducting a randomized controlled trial (RCT) to examine the effects of a new volunteer-supported model to improve cognitive function in MCI persons through the promotion of an active lifestyle. We noticed that sleep problems are highly prevalent among this vulnerable group, and their motivation is low. As such, this team of investigators, which has a strong research track record and expertise in delivering psychosocial interventions, care of persons with MCI and dementia and chronic disease management using the empowerment-based educational model, developed an evidenced-based CBT-I intervention featuring the empowerment approach to improve sleep quality and cognition in persons with MCI. The PI and the Co-I ([name]) have successfully used the empowerment model to promote self-care among patients with heart failure. Indeed, the co-investigators have extensive research and clinical experience in working with people with MCI and dementia. The Co-I ([name]), a nursing academician specializing in gerontology, has established an online CBT-based website (Sweet Dream) to fight against insomnia in the older population in Hong Kong and has tested the effects of an activity-based intervention for older people with sleep complaints. Another Co-I ([name]) is a psychologist with substantial research experience working with people with MCI and dementia. This study proposes to address a neglected area in the literature and to test the effects of an empowerment-based CBT-I for MCI persons on their sleep and cognition.

